# Allowed to be up to 3 days early or late

## Allowed to be up to 1 day early or late

§ Allowed up to 6 hours early or late

## 6. SUBJECTS

### 6.1 Anticipated number of research subjects

The sample size calculation does take into account a 30% patient attrition rate (withdrawal and loss to follow-up), since this involves a study with multiple time points for data collection up to 12 weeks. From other similar studies we are aware that loss to follow-up is relatively high in this group of patients. Patients will be recruited from the adult (age 18+) population routinely seen by the evaluating clinical staff members. The primary outcome measure is based on knee/leg (ie wound site) pain experienced 5-days post-surgery based on the VDS pain scale 'at rest'. The hypothetical difference in pain perception is 1.5 on a 10 cm scale which equates to a significant 'minimally clinically important difference' for pain (Kelly 2001; Lee et al 2003; Tashjian et al 2009). The values and differences observed in the ROBOT trial will be used for reference.

The non-parametric two-sided Mann-Whitney u-test is applied because the data is ordinal; 80% power and 5% significance is also applied. A priori power calculations using GPower 3.1 software, result in the following sample size summarized in Table 3.

Analysis will be performed on an intention-to-treat basis, although the number of days that a participant has worn a bandage will be recorded.

Table 4, Sample size calculation

	Mean pain score at 5 days post-op	Standard Deviation
Arm A (hypothetical)	5.0	2
Arm B (hypothetical)	3.5	2
	Power beta of 80%, Alpha p-value of 0.05, Effect size 0.75  Sample size required without any drop-out: 62 Sample size with 30% attrition rate included: 88  Total of 88 patients: 
 
- 44 Patients to receive AIRCAST® KNEE CRYO/CUFF™ device (current standard care, control arm)
 
- 44 Patient to receive VPULSE® (intervention arm)
 
	

The CONSORT guidelines require a statement on the number of patients assessed for eligibility (Schulz, Altman & Moher 2010). The number of patients screened but who did not meet the inclusion criteria or who declined to participate will be recorded, as will any patients who are lost to follow-up (Appendix 3).

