Secondary objectives	
Post-operative patient-reported outcome measures:
 
Prior to surgery and 24hrs, 3, 5, 12 days, and 6 weeks post-surgery
 
 
- Pain perception, using VDS pain (at rest and walking) and short form McGill pain questionnaire
 
 
Prior to surgery as baseline, and 6 and 12 weeks post-surgery, knee function and quality of life measurements
 
 
- Knee and Osteoarthritis Outcome Score (KOOS)
 
- Range of motion of the affected limb
 
 
Descriptive safety overview at 30 days and 12 weeks post-surgery:
 
 
- Readmitted to theatre and/or hospital
 
- Infection of wound site
 
- Diagnosed with pulmonary embolism or deep vein thrombosis.
 
 
Patient satisfaction survey at 5 days post-surgery

Sponsor	North Cumbria Integrated Care NHS Foundation Trust
Manufacturer & research grant provider	Joint Operations, supplier of VPULSE® active compression & cooling therapy device. Contact: [name], Business Development Manager, [contact] , email [contact] , www.jointoperations.co.uk , [name]
Chief Investigator	[name], consultant Orthopaedic Surgeon. North Cumbria Integrated Care NHS Foundation Trust. Phone numbers: [name], [contact]
Co-investigators	[name], consultant Orthopaedic Surgeon. North Cumbria Integrated Care NHS Foundation Trust, [contact]

	
[name], Orthopaedic Specialist Practitioner, North Cumbria Integrated Care NHS Foundation Trust, [contact]
 
[name] PhD, Science & Innovation Manager, [contact]; [contact] North Cumbria Integrated Care NHS Foundation Trust
 
[name], Orthopaedic Specialist Practitioner, North Cumbria University Hospitals NHS Trust, [contact]
 
[name], Advanced Nurse Practitioner, North Cumbria University Hospitals NHS Trust, [contact]

Organisation where research will take place	
North Cumbria Integrated Care NHS Foundation Trust Orthopaedics Department [name]

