### **3. INVESTIGATIONAL DEVICE & INTERVENTION**

#### **3.1 Intervention**

##### **3.1.1 Control (standard care) arm - AIRCAST® KNEE CRYO/CUFF™**

Once the operation is finished, a wound dressing is applied and a standard bandage is applied. It consists of one layer of soft synthetic bandage, stretching from proximal tibia to distal femur covered by a further layer of crepe bandage prior to or after tourniquet deflation, with 50% overlap of each layer. Once transferred to the ward for recovery, this standard bandage will be removed and AIRCAST® KNEE CRYO/CUFF™ cryotherapy is applied to the patient's index knee. This is a sleeve containing iced water and it will be utilised for up to 48 hours post-operation or until patient discharge, whichever of the two is sooner.

The CRYO/CUFF™ is designed to combine the therapeutic benefits of controlled cold compression to minimise hemarthrosis and swelling and reduce pain. The cuff is anatomically designed to completely fit the knee providing maximum coverage of the whole joint and allowing the whole surface area to have the continual cooling benefit of cryotherapy. The cuff is attached to the Gravity Aircast Cryo/Cuff Cooler and will hold water and ice needed for six to eight hours of cryotherapy.

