### **5.5 Outcome measures**

#### **5.5.1 Primary outcome measures**

To determine the level of operation-site related pain experienced at day 2 post-operation and to compare the average pain scores of patients in the control and intervention arm respectively, through administration of 10 cm visual descriptor scale (VDS) for pain.

The study is powered to detect the established minimal clinically important difference (MCID) of 1.5 cm on a 10 cm VDS pain.

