#### **5.5.2 Secondary outcome measures**

All the outcome measures are summarised in Table 3.

Table 3. Overview of measurements

Weeks	-12 weeks to day of surgery	0 surgery	24hrs §	3 days ##	5 days ##	12 days #	6 weeks*	12 weeks
Application device post surgery		X	x					
VDS pain scale (at rest)	X		x	X	X	X	X	
VDS pain scale (walking, if capable to stand)	X		x	X	X	X	X	
McGill pain questionnaire	X		x	X	X	X	X	
Limb range of motion	X						X	
KOOS score	X						X	X
Patient satisfaction questionnaire re device use					X	X (if not returned yet at 5 days)		

\* Allowed to be up to 2 weeks early or late

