## 8.2 Primary outcome statistics

To determine the level of operation-site related pain experienced at day 2 post-operation and to compare the average pain scores of patients in the control and intervention arm respectively, through administration of 10 cm visual descriptor scale (VDS) for pain.

The study is powered to detect the established minimal clinically important difference (MCID) of 1.5 cm on a 10 cm VDS pain.

The average difference between time points will be calculated per group, 2 days post-surgery being the primary endpoint. 24hrs, 3, 5, 12 days and 6 weeks post-surgery will also be analysed. To compare the groups, the Mann-Whitney U-test will be applied.

To avoid relying on one outcome measure related to pain, at 3, 5, 12 days, and 6 weeks post-surgery pain perception will also be measured using the short form McGill pain questionnaire. Again, to compare groups the Mann-Whitney U-test will be applied.

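### The primary pain endpoint is day 2 in four places and day 5 in the sample-size section, and no pain assessment is scheduled at day 2

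*Protocol*

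**What the plan says.** Four places put the primary comparison at day 2. The summary's primary objective does so for pain at rest, and the lay summary uses 48 hours. Section 5.5.1 reads "To determine the level of operation-site related pain experienced at day 2 post-operation". Section 8.2 has "2 days post-surgery being the primary endpoint. 24hrs, 3, 5, 12 days and 6 weeks post-surgery will also be analysed", which treats day 2 as distinct from the other days.

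Section 6.1 disagrees: "The primary outcome measure is based on knee/leg (ie wound site) pain experienced 5-days post-surgery". Table 4, which carries the planning values of 5.0 and 3.5 with a standard deviation of 2, heads its column "Mean pain score at 5 days post-op".

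The summary schedules pain measurement as follows: "Prior to surgery and 24hrs, 3, 5, 12 days, and 6 weeks post-surgery". In section 5.5.2, Table 3, the row beginning "VDS pain scale (at rest" is marked at those same times, with no column for day 2. Section 5.4 mentions 24 hours and days 3, 5 and 12. The Table 3 footnotes give the 24-hour assessment 6 hours either way, and days 3 and 5 the rule "Allowed to be up to 1 day early or late".

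Two further facts bear on how the days differ. The form in Appendix 1 asks about pain over the last day. For the control device, section 3.1.1 says "it will be utilised for up to 48 hours post-operation or until patient discharge, whichever of the two is sooner".

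**The concern.** A trial needs one primary outcome, and its schedule must collect it. This plan declares two primary days, and the one it declares most often has no visit.

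Followed as written, the primary analysis in section 8.2 has no scheduled data. The team would have to use day 3 in place of day 2, fall back on day 5 because section 6.1 says so, or analyse only those participants whose day-3 form happened to come in early. Each choice changes the declared endpoint, and the choice would be made after data had been collected in a trial where participants know their device and report their own pain.

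The days are not interchangeable. With a one-day recall, a 48-hour reading covers roughly 24 to 48 hours, within the maximum period of device use stated for the control arm. A nominal day-3 reading covers roughly 48 to 72 hours, after that maximum. A day-5 reading begins its recall about two days after it and is taken about three days after it.

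The sample-size text adds to the problem, because it attaches the planning assumptions to a day other than the declared endpoint.

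**Working it through.** **Step 1. Which day is primary.**

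| Place in the Protocol | Primary day |
|---|---|
| Summary, primary objective | day 2 |
| Section 1, lay summary | 48 hours |
| Section 5.5.1 | day 2 |
| Section 8.2 | day 2 |
| Section 6.1, text | day 5 |
| Section 6.1, Table 4 (planning means) | day 5 |

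Only day 2 and day 5 are ever named as primary.

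**Step 2. Does any post-operative window cover day 2?**

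| Nominal time | Allowed window | Covers day 2? |
|---|---|---|
| 24 hours | 24 − 6 = 18 h to 24 + 6 = 30 h | No; it closes 48 − 30 = 18 h short |
| Day 3 | 3 − 1 = day 2 to 3 + 1 = day 4 | Only at its earliest edge |
| Day 5 | 5 − 1 = day 4 to 5 + 1 = day 6 | No |
| Day 12 | 12 − 3 = day 9 to 12 + 3 = day 15 | No |
| 6 weeks | 4 to 8 weeks | No |

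The day-3 form may be completed on day 2, but nothing requires this and nothing makes such a form the primary value. Section 8.2 lists day 3 separately from the day-2 endpoint, so day 3 cannot be read as another name for it. The number of participants with a scheduled day-2 score is 0 of 88.

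**Step 3. Reproduce the sample size.** Inputs from section 6.1 and Table 4: difference 5.0 − 3.5 = 1.5 cm, standard deviation 2 cm, effect size 1.5/2 = 0.75, two-sided 5% level, 80% power, Mann-Whitney test.

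Method: noncentral t, with the per-arm size multiplied by the asymptotic relative efficiency of the Mann-Whitney test for normal data, 3/π = 0.955.

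- 31 per arm: effective size 31 × 0.955 = 29.60; degrees of freedom 2 × 29.60 − 2 = 57.2; noncentrality 0.75 × √(29.60/2) = 2.885; critical value 2.002; power 0.810.
- 30 per arm: power 0.796, below target.

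So 31 per arm, or 62 in total, matches the stated figure. With 30% attrition, 62/0.70 = 88.6, which is 89 if rounded up, against 88 stated. That difference is immaterial.

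**Step 4. What follows if the standard deviation differs at day 2.** The Protocol gives no day-2 standard deviation. The values below other than 2 cm are assumptions. The difference stays at 1.5 cm with 31 per arm, and the method is that of step 3.

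| Assumed SD (cm) | Effect size | Power |
|---|---|---|
| 1.5 | 1.00 | 97% |
| 1.75 | 0.86 | 90% |
| 2.0 (as planned) | 0.75 | 81% |
| 2.5 | 0.60 | 62% |
| 3.0 | 0.50 | 47% |

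The range runs both ways, and nothing in the Protocol says where in it day 2 lies.

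**The case against.** Five points can be made for the plan.

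- **Some day-2 readings will exist.** A reader might infer that the primary outcome would be absent from the data altogether. The day-3 window rules that out, because a form completed a full day early falls on day 2. What stands is that such readings would be incidental, filed as day 3 and available for an unknown subset.
- **No loss of power is shown.** It is tempting to conclude that the trial is underpowered for its real endpoint. The documents do not support that. Table 4 labels both arms hypothetical, the 1.5 cm is justified as a minimal clinically important difference and not as an effect seen at day 5, and the summary gives the same 1.5 cm and 2 cm beside a day-2 objective. The sample-size fault is a day label that contradicts the endpoint.
- **The device may already be off at day 2.** A reader might call day 2 a purely on-treatment measure. Section 3.1.1 ends use at discharge if that comes before 48 hours, and the introduction says stays rarely exceed 2 days. The limit is written for the control arm only; for VPULSE it is inferred from the statement in section 3.1.2 that the arms are otherwise handled alike. The days still differ in what they measure, but less cleanly than a simple on/off contrast.
- **The analysts are blinded.** Section 6.1.1 says so, which limits the scope for a choice of day driven by the results. It does not decide which day is primary, and it cannot supply a missing reading.
- **Other documents may help.** The participant flowchart in Appendix 2 is not readable here, and a separate statistical analysis plan may exist. However, section 5.5.2 says Table 3 summarises all outcome measures, and an analysis plan cannot add a reading that was never scheduled.

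**Conclusion.** The contradiction is real and must be fixed. Day 2 is primary in four places, and day 5 is primary in section 6.1 and Table 4. No pain schedule in the readable text has a day-2 assessment. The declared primary outcome would therefore not be collected systematically: 0 of 88 participants have it scheduled.

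The conclusion does not extend to the number of patients. The 62 stands at 81% power, provided that the 1.5 cm difference and 2 cm standard deviation hold at whichever day is chosen. Whether they hold at day 2 cannot be judged from the Protocol; the 97% to 47% range shows sensitivity to an assumption and is not a forecast. Nor are there three or four competing primary endpoints. Two days are named as primary, and 24 hours and day 3 come in only as possible substitutes.

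**What to change.** Amend the Protocol as follows.

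1. State one primary time point in the summary, lay summary and sections 5.5.1, 6.1 and 8.2. Day 2 (48 hours) has most support in the text.
2. Specify pain at rest wherever the primary outcome is defined. The summary and section 6.1 do so; sections 5.5.1 and 8.2 do not.
3. If day 2 is kept, add a column for pain at rest at that time, with a stated window, to Table 3 and to the summary's schedule. The 6 hours either way already used at 24 hours is one possible window; the choice is the sponsor's.
4. Say which reading counts as the primary value, and whether a day-3 form completed early may ever stand in for it.
5. Align the text of section 6.1 and the column heading of Table 4 to the chosen day. Confirm that a standard deviation of 2 cm is reasonable then, for example from the sponsor's reference trial if it has early post-operative data, or restate the power.

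The cost is amended wording and one short form per participant, which section 5.4 already allows by phone, e-mail or mail. Some participants will be home by 48 hours, so contact at that time needs planning. No extra patients are needed if the planning values hold.

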### 6.1.1 Randomisation

Following written consent patients will be allocated at random to the one of two treatment arms, the control AIRCAST® KNEE CRYO/CUFF™ or VPULSE® intervention group, using a non-restricted randomised sequence generated for the whole sample using a free ware randomisation programme, see <https://www.sealedenvelope.com/> . Each next randomisation allocation will be obtained from the sealedenvelope.com account for this ALASKA trial.

As the study involves different looking cooling devices, it is not possible to achieve blinding for the participants. However, statistical analysis is carried out blinded to group allocation, by persons who have not had contact with study participants.

## 6.2 Eligibility criteria

### 6.2.1 Inclusion criteria

- Patient who is listed for:
  - Knee arthroplasty (replacement) surgery, either partial or total knee replacement (unilateral).
- Clinical indication, in the opinion of the treating surgeon, that compression & cooling therapy may be of benefit to the patient
- Adult patients aged > 18 years

- Mental capacity to give written informed consent

### 6.2.2 Exclusion criteria

- Under the age of 18 years
- Unable to fully understand the consent process and provide informed consent due to either language barriers or mental capacity
- Revision of previous knee replacement or osteotomy on the index leg.
- Limited life expectancy, i.e. undergoing palliative care
- Any condition that is associated with excessive bleeding, coagulation abnormalities or any other significant haematological condition (e.g. Factor V Leiden, haemophilia).
- Cardiovascular or vascular condition that in the opinion of the treating surgeon contraindicates the use of compression bandaging, including moderate to severe peripheral arterial disease, venous leg ulcer, high dose anti-coagulant medication
- Any skin or other condition that contraindicates the use of compression and cooling therapy.
- Patients who are participating in another interventional research study involving an investigational product related to the knee procedure and its aftercare.
- The patient has concurrent (medical) conditions that in the opinion of the investigator may compromise patient safety or study objectives.
- Patient has practical or mobility issues which will prevent them from removing the device themselves

### 6.3 Early withdrawal of subjects

Patients have the right to withdraw from the trial at any time and without giving any reason. If a patient withdraws from the trial, any and all information gathered prior to the withdrawal will be excluded in the analysis, no further data collection will occur. If a patient does not attend a planned follow-up appointment then two more attempts will be made to contact the patient regarding the study. If still no contact can be made then the patient is deemed lost to follow-up and any collected study data will be retained.

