### **5.3 Consent and recruitment**

Those eligible will be approached and provided with an information pack and consent form, which will be signed to indicate that informed consent has been given. Patients will be given ample time to consider taking part, more than 24 hours if they wish. The study will be first mentioned at an orthopaedics out-patient clinic visit. The direct healthcare professional will first approach a patient about the study, and after verbal consent by the patient the healthcare professional themselves or a member of the research team can go through the informed consent process.

Patients are also allowed to consent to taking part when first approached as long as the study has been discussed with the patient and they have been given time to read the patient information leaflet and opportunity to ask any questions that they may have. Participants will receive no incentives and consent will be regarded as a process and not a one-off event. Participants are free to withdraw from the study at any time without the need to give any reasons for withdrawal. Their standard of care will not be affected by either declining to participate in the study or withdrawing during participation. Data collected up to the date of withdrawal will be retained for analysis.

Participants will be randomised to either the control group (Cryo/Cuff) or the intervention group (VPULSE) any time up until the day of surgery.

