### **5.4 Follow-up**

Patients are in the study for a period of 12 weeks. Thereafter, the patient will be followed up as they would be in normal clinical practice. Study visits are aligned to hospital/clinic visits where possible. Baseline data can be collected on the day of surgery (prior the actual operation), and 12 day and 12 week post-surgery data can be collected when the patient attends for standard follow-up in the orthopaedics out-patient department. The data at 24 hrs, day 3, 5, and 12 falls outside these dates. For all outcome measures, data can be collected over the phone, via e-mail or by mail (whichever is preferred by the patient – mail is by use of freepost, to avoid patients incurring any costs). The researcher can also send reminders to the participant regarding the completion of certain outcome data at the aforementioned follow-up time points.

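### Section 6.3 excludes withdrawn participants' data from the analysis, section 5.3 retains them and section 6.1 states intention-to-treat; the three rules cannot all be followed

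*Protocol*

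**What the plan says.** Three statements in the protocol bear on the same data.

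- Section 5.3 (Consent and recruitment), on withdrawal: "Data collected up to the date of withdrawal will be retained for analysis".
- Section 6.3 (Early withdrawal of subjects), on withdrawal: "any and all information gathered prior to the withdrawal will be excluded in the analysis, no further data collection will occur".
- Section 6.1 (Anticipated number of research subjects), on the analysis principle: "Analysis will be performed on an intention-to-treat basis".

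The same paragraph of 6.3 handles non-responders the other way. If two further contact attempts fail, "then the patient is deemed lost to follow-up and any collected study data will be retained".

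On timing, section 8.2 has "2 days post-surgery being the primary endpoint", while Table 4 in section 6.1 is headed "Mean pain score at 5 days post-op", and Table 3 has no day-2 column. That inconsistency is a separate matter. Under either reading the primary pain score falls in the first days, whereas section 5.4 says "Patients are in the study for a period of 12 weeks".

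The sample size carries a "30% patient attrition rate (withdrawal and loss to follow-up" allowance, so it covers both kinds of drop-out together.

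**The concern.** Sections 5.3 and 6.3 give opposite instructions for the same records, and a statistical analysis plan that follows either one contradicts the other.

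The choice affects the primary analysis. Most of the 12 weeks in which a participant can withdraw comes after the primary pain score is due. Under 6.3, someone who gives that score and withdraws at week 8 is taken out of the early comparison because of something that happened long afterwards. This is selection on a post-randomisation event, and it does not fit the intention-to-treat statement. It also separates two similar people: one who announces a withdrawal loses a recorded score, and one who stops answering keeps it.

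Two things are at stake. The first is precision, because observed outcomes are discarded. The second is possible bias: participants know their device (section 6.1.1), so the rate of withdrawal and the reasons for it could differ by arm. Leaving the rule open also means that the analysis set could be settled after data have been seen, for example around the interim look at 50% of the sample (section 9).

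**Working it through.** **Inputs from the protocol.** Difference 1.5 cm, SD 2 cm, so d = 1.5/2 = 0.75; two-sided Mann-Whitney test; alpha 0.05; power 80%; 62 evaluable participants; 88 with 30% attrition, 44 per arm (summary and section 6.1). Withdrawal rates by arm are not given, and neither is the split of the 30% between withdrawal and loss to follow-up. Both are assumed below.

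**Step 1: reproduce the plan's figure.** Take the two-sample t-test power from the noncentral t distribution and scale n by the Mann-Whitney asymptotic relative efficiency for normal data, 3/π = 0.955:

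N = n × 3/π; df = 2N − 2; noncentrality = 0.75 × √(N/2).

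At n = 31 per arm: N = 29.60, df = 57.2, noncentrality = 2.885, critical t = 2.002, power = 81.0%. This is the smallest n that reaches 80%, so the total is 62, as in the plan. Inflation gives 62/0.7 = 88.6, against 88 in the plan.

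**Step 2: power under the two rules.** The formula is the same; only the number of analysed scores changes.

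| Scores analysed per arm | Situation | Noncentrality | Power |
|---|---|---|---|
| 44 | every early score observed and kept (5.3 rule) | 3.438 | 92.5% |
| 40 | about 10% excluded | 3.278 | 89.9% |
| 37 | 15% excluded: 44 × 0.85 = 37.4, i.e. half of the allowance is active withdrawal (assumption) | 3.152 | 87.5% |
| 31 | the whole allowance is active withdrawal: 0.30 × 88 ≈ 26, or 13 per arm | 2.885 | 81.0% |

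**Step 3: when exclusion biases the difference.** If a fraction w of an arm is excluded and those excluded score g cm worse than those kept, the mean of those kept is lower than the full-arm mean by w × g. With the same g in both arms, the between-arm difference shifts by (w₁ − w₂) × g. The shift is zero when g = 0 (withdrawal unrelated to pain) or when w₁ = w₂. With assumed rates of 15% and 5% and g of 2 to 3 cm, it is 0.10 × 2 to 0.10 × 3 = 0.2 to 0.3 cm.

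**Step 4: simulation.** There were 4,000 trials per row, with 44 per arm, normal scores, SD 2 and a Mann-Whitney test. Withdrawal occurs after the score. Where it is pain-related, the weight for withdrawing is multiplied by e for each SD of extra pain. All rates are assumptions. Differences are control minus VPULSE.

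| True difference | Withdrawal, control / VPULSE | Pain-related | Difference after exclusion | Rejection rate after exclusion |
|---|---|---|---|---|
| 0 | 10% / 10% | no | −0.01 cm | 4.7% |
| 0 | 15% / 15% | yes | 0.00 cm | 5.8% |
| 0 | 5% / 15% | yes | 0.21 cm | 8.1% |
| 0 | 0% / 20% | yes | 0.39 cm | 13.2% |
| 0 | 10% / 30% | yes | 0.40 cm | 14.3% |
| 1.5 cm | 30% / 30% | no | 1.50 cm | 80.6% |
| 1.5 cm | 15% / 15% | yes | 1.50 cm | 89.1% |
| 1.5 cm | 5% / 15% | yes | 1.72 cm | 96.5% |
| 1.5 cm | 15% / 5% | yes | 1.29 cm | 80.5% |

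When every observed score was analysed, the difference stayed within about 0.01 cm of the truth, the rejection rate was 4.3% to 5.0% under no effect, and power was about 92% to 93% at 1.5 cm.

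**The case against.** The best defence is that 6.3 contains a drafting slip. *Excluded in* is an odd phrase; *included in* would agree with 5.3, with intention-to-treat and with the next rule in the same paragraph. That may well be so. It does not remove the point, because 6.3 is the dedicated withdrawal section and, read literally, draws a distinction between withdrawal and loss to follow-up.

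A reader might infer more than the documents support in four respects.

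- *That the full 30% attrition is applied to the early endpoint.* It is not. The allowance covers loss to follow-up as well, and 6.3 keeps those participants' data. The protocol gives no split; it says only that loss to follow-up is relatively high in this group.
- *That the trial becomes underpowered.* Within the planned attrition it does not. Even the bound of 31 per arm is the 62 evaluable participants that the plan requires, so 6.3 uses up reserve power and nothing more.
- *That the comparison is biased as a matter of course.* It is not. Step 3 and the zero-shift rows in Step 4 show that bias needs withdrawal that is both related to pain and unequal by arm.
- *That the data are deleted.* The text leaves them out of the analysis; it does not say they are destroyed.

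There is also a fair argument that device-related bias may be modest here. Section 3.1.1 limits use of the control device to 48 hours or discharge, and section 3.1.2 says the arms are otherwise the same. Withdrawal during device use would mostly come before a day-2 score exists, and withdrawal weeks later has a less direct link to the device. This lowers the likelihood of a large bias but does not rule it out.

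**Conclusion.** The contradiction stands and is unresolved in the protocol. As written, 6.3 would remove observed primary outcomes because of a later event, against both 5.3 and the stated intention-to-treat principle.

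If anyone withdraws after giving a score, the sure cost is lost precision. Power falls from 92.5% to about 87.5% if half of the allowance is active withdrawal, and to 81% as a worst-case bound that still meets the 80% target. These figures assume d = 0.75 and roughly normal scores.

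Bias is possible but conditional. Under assumed pain-related withdrawal of 5% in one arm and 15% in the other, the difference moves by about 0.2 cm (0.2/1.5 = 13% of the target difference) and the type I error rises to about 8%. If withdrawal is unrelated to pain, or equally frequent and similarly related to pain in both arms, the difference does not shift, although the rejection rate in the equal, pain-related case was slightly above nominal at 5.8%. The documents give no basis for predicting which pattern will occur. The planned 62 and 88 are unaffected.

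**What to change.** Replace the exclusion sentence in section 6.3 with the rule already in 5.3: data collected up to withdrawal are retained and analysed in the randomised arm, and only further collection stops. This also brings withdrawal into line with the handling of loss to follow-up. If any participant asks for their data to be removed, report the number by arm.

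Check that the participant information and consent wording agrees with the revised rule. Those texts are not available here, so what participants were told is unknown.

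The cost is one sentence plus the review and approval that section 10.1 requires before departing from the approved protocol. No sample size or test changes. It should be settled before any outcome data are analysed, including the interim analysis at 50% of the sample.
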